### 10.2. TABLES

Tables will present Baseline and Week 12, unless specified otherwise. Tables will present the 7 treatment groups.

Analysis population: ITT.

#### **Table 14.2.3.1: Pharmacodynamics: YKL-40: Descriptive statistics**

Descriptive statistics of actual values, changes from baseline and percent changes from baseline.

#### **Table 14.2.3.2: Pharmacodynamics: YKL-40: Summary with overall p-value and pairwise comparisons versus placebo**

Analysis model is similar to DAS28(CRP). Only one time point: Week 12.

#### **Table 14.2.3.3: Pharmacodynamics: YKL-40: Exploratory pairwise comparisons among the dose groups within each regimen**

**Table 14.2.3.4: Pharmacodynamics: YKL-40: Exploratory pairwise comparisons between regimens within each daily dose level**

**Table 14.2.3.5: Pharmacodynamics: YKL-40: Descriptive statistics for Week 12 ACR20 responders versus non-responders**

Same as previous table, but split up for Week 12 ACR20 responders and non-responders.

**Table 14.2.3.6: Pharmacodynamics: YKL-40: Descriptive statistics for Week 12 ACR50 responders versus non-responders**

**Table 14.2.3.7: Pharmacodynamics: YKL-40: Descriptive statistics for Week 12 ACR70 responders versus non-responders**

**Table 14.2.3.8: Pharmacodynamics: YKL-40: Correlation with ACR20/50/70**

Relationship between the change from baseline in PD marker and ACR20 will be investigated via a logistic regression model on the ACR20 responses, with the following factors in the model: treatment groups, baseline YKL-40, change from baseline in YKL-40. ACR20 and YKL-40 will be taken from the same visit.

Same for the ACR50 and ACR70.

**Table 14.2.3.9: Pharmacodynamics: YKL-40: Correlation with continuous efficacy parameters**

Relationship between the change from baseline in PD marker and the change from baseline in efficacy parameters will be investigated via Pearson's correlation coefficient as provided by SAS PROC CORR. Efficacy parameters and YKL-40 will all be taken from the same visit.

The following efficacy parameters will be tested:

- ACR20 components: TJC68, SJC66, the 3 VAS scores, CRP and HAQ-DI.
- Summary scores: DAS28(CRP), CDAI and SDAI.

### 10.3. FIGURES

**Figure 14.2.3.1: Pharmacodynamics: YKL-40: Mean plot over time**

Line plot baseline-W12, like for the efficacy parameters. Plot will contain the 7 groups.

Analysis population: ITT.

**Figure 14.2.3.2: Pharmacodynamics: YKL-40: Correlation plots versus efficacy**

Correlation scatterplots of the percent changes from baseline in YKL-40 versus:

- Percent change from baseline in: TJC68, SJC66, the 3 VAS scores, CRP and HAQ-DI
- Percent change from baseline in DAS28(CRP), CDAI and SDAI

Efficacy parameters and YKL-40 will all be taken from the same visit. Each plot on a new page, using different plot symbols per group. Because of the large number of groups, put the placebo with the qd dose groups on one plot, and the placebo with the bid dose groups on a second plot.

Analysis population: ITT.

## 10.4. LISTINGS

### Listing 16.2.8: Pharmacodynamics: YKL-40

Listing per treatment group, per subject and per time point of the YKL-40 results: actual values, changes from baseline and percent changes from baseline.

Population: ITT.

## 11. DEFINITIONS OF PK/PD TABLES, LISTINGS AND FIGURES

These analyses will be described in a separate SAP. A separate report will be written based on the analysis performed by [REDACTED].

## 12. DEFINITIONS OF SAFETY TABLES, LISTINGS AND FIGURES

Mock tables, listings and figures are provided in a separate document.

All analyses will be run on the Safety population, unless specified otherwise.

### 12.1. ADVERSE EVENTS

#### 12.1.1. Treatment-Emergent Principle

All adverse events with onset on or after first dosing are considered treatment-emergent adverse events (TEAE).

Adverse events will be placed into analysis periods according to their start date. Analysis periods: see section 3.2. The AE will only be presented in the analysis period during which it started. Rule: period start date  $\leq$  AE start date  $\leq$  period stop date.

In case the AE start date is incomplete, a worst-case allocation will be done according to the available parts of the AE start date. When too much of the AE start date is missing to apply the above rules, the AE will be allocated to:

- the first treatment period, in case the doubt is between the screening and first treatment analysis period;
- both treatment periods, in case the doubt is between both treatment periods.

All adverse events emerging during the screening period will only be listed, not presented in any of the tables. These events are not TEAEs. All tables will present TEAEs only.

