#### **Adverse Event**

An AE is any untoward medical occurrence in a clinical study subject administered a medicinal (investigational or noninvestigational) product. An AE does not necessarily have a causal relationship with the treatment. An AE can therefore be any unfavorable and unintended sign (including an abnormal finding), symptom, or disease temporally associated with the use of a medicinal (investigational or noninvestigational) product, whether or not related to that medicinal (investigational or noninvestigational) product.

This includes any occurrence that is new in onset or aggravated in intensity or frequency from the baseline condition (signing the ICF) or abnormal results of diagnostic procedures, including laboratory test abnormalities.

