### **Intensity of an Adverse Event**

Each AE must be rated on a 3-point scale of increasing intensity:

- Mild: Transient or mild discomfort; no limitation in activity; no medical intervention/therapy required.
- Moderate: Mild to moderate limitation in activity; some assistance may be needed; no or minimal medical intervention/therapy required.
- Severe: Marked limitation in activity; some assistance usually required; medical intervention/therapy required, hospitalization possible.

If there is a change in intensity of an ongoing AE, it must be recorded as a separate event.

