## **3.2. ANALYSIS PERIODS FOR NON-VISIT DATA**

These analysis periods are to be used for allocation of adverse events and concomitant medications into periods.

Analysis period	Period start date	Period end date
Screening	Date of signing the initial ICF.	First study drug administration date – 1 day.
First 12 weeks	First study drug administration date.	Date of the W12 visit.
Second 12 weeks	Date of the W12 visit + 1 day.	Max ( trial termination date ; date of last dose + 30 days ).
Full 24 weeks	First study drug administration date.	Max ( trial termination date ; date of last dose + 30 days ).

The trial termination date is the date of last contact with the subject, as recorded in the eCRF.

Note that the last analysis period in case of early termination will always be ended by: *Maximum ( trial termination date ; date of last dose + 30 days)*. In case the subject rolls over to DARWIN3, the trial termination date will be used (no 30 days will be added since that would be during DARWIN3).

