### 12.1.3. Worst-Case Principle

When cross-tabulating AE preferred terms versus an AE attribute (e.g., intensity), the worst-case is always applied within each analysis period. I.e., when a subject has two times the same AE preferred term in the same analysis period, then the subject is reported only once: only with the worst intensity. If this happens in two different analysis periods, the AE is reported twice: once in each analysis period.

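### Because each intensity change is a new AE record and the SAP goes by record start date, an AE that merely eases can count as treatment-emergent across first dose, or be counted again across Week 12

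*SAP*

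**What the plan says.** The protocol's section on the intensity of an adverse event, within 8.7.1.4.1.1, states: "If there is a change in intensity of an ongoing AE, it must be recorded as a separate event". No direction is given, so easing is covered as well as worsening. AEs are collected from signature of the consent form (Protocol 8.7.1.4.1.2), so some begin before first dose.

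SAP 12.1.1 defines emergence by onset alone: "All adverse events with onset on or after first dosing are considered treatment-emergent adverse events (TEAE". On allocation to periods it states: "The AE will only be presented in the analysis period during which it started". On events before dosing it states: "All adverse events emerging during the screening period will only be listed, not presented in any of the tables".

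In SAP 3.2 the second 12 weeks starts at "Date of the W12 visit + 1 day". The full 24 weeks is a separate analysis period that starts at first dose. SAP 12.1.7 asks for the AE tables over the first 12 weeks, the second 12 weeks and the full 24 weeks, with some subgroup tables for the full period only.

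SAP 12.1.3 handles repeats. Where the same preferred term recurs for a subject within one period, "then the subject is reported only once: only with the worst intensity". Across periods: "If this happens in two different analysis periods, the AE is reported twice: once in each analysis period".

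For the 24-week safety tables, SAP 2.1.2 and 4.5.2 give subjects who switch at Week 12 their own columns by treatment sequence.

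**The concern.** The recording rule guarantees split records, and the analysis rule treats each record as if it were a fresh event. Neither document says that a continuation record inherits the onset of the event it continues, or that intensity must have risen. An improvement can therefore be scored as an emergent event.

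The SAP applies a worsening test elsewhere. A treatment-emergent CTCAE grade must exceed the baseline grade (Table 14.3.2.8), an ATP III class must be of higher category (Table 14.3.2.11), and a QT abnormality must be higher than at baseline (Table 14.3.3.4). AEs have no counterpart.

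Attribution is what is at stake. An event that began before any study drug could be charged to the randomized arm. An event that began on placebo or a low dose could appear among the events of the period after the switch. The placebo-switch columns describe a first exposure to GLPG0634 and are small, so single records show.

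**Working it through.** The plan states no figure on this point, so there is none to reproduce. The check applies the SAP rules to example AE histories and then works out the scale.

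**Rules applied.** A record is a TEAE if its start day is 1 or later. It falls in the first 12 weeks up to and including the Week 12 visit (Day 85 here) and in the second 12 weeks after that. Each preferred term counts once per subject per period. It is assumed that a new record starts on the day the intensity changes.

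| History | Records by start day | First 12 weeks | Second 12 weeks | Full 24 weeks |
|---|---|---|---|---|
| A. Screening AE, eases after dosing | Day -5 severe; Day 5 mild | 1 | 0 | 1 |
| B. Eases within the first period | Day 20 moderate; Day 40 mild | 1 | 0 | 1 |
| C. Placebo subject, eases after the switch | Day 70 moderate; Day 100 mild | 1 | 1 | 1 |
| D. Same onset as C, intensity unchanged | Day 70 moderate | 1 | 0 | 1 |

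If the records were linked and only worsening counted, A would give 0, 0, 0 and C would give 1, 0, 1. B and D would not change. The distortion therefore lies in A (the first-dose boundary) and C (the Week 12 boundary). In B the easing adds a record and a listing line, but no subject-level count. In C the full-24-weeks count is right, because that span is one analysis period and the two records collapse.

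**Scale of a placebo-switch column.** Inputs:
- 85 subjects randomized to placebo (Protocol 8.5.4).
- Placebo ACR20 response of 20% to 40% at Week 12, the planning assumption in Protocol 8.8.2.
- Switching applies to placebo subjects without 20% improvement in both joint counts. Every ACR20 responder has that improvement, so the number of switchers is at most 85 x (1 - ACR20 rate).
- A 1:1 split between the two switch doses. This is an assumption; the documents do not state the ratio.

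Results:
- ACR20 rate 20%: at most 85 x 0.80 = 68 switchers, or 34 per column. One subject is 100/34 = 2.9 percentage points.
- ACR20 rate 40%: at most 85 x 0.60 = 51 switchers, or 25.5 per column. One subject is 100/25.5 = 3.9 percentage points.

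These are upper limits on column size, so in a smaller column one record moves the rate further.

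**The case against.** Several stronger readings are tempting, and the documents do not support them.

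- **That TEAE incidence is inflated throughout, in all arms.** The summary tables count subjects with at least one event, and SAP 12.1.3 collapses repeats within a period. Only the first-dose boundary reaches every arm in the tables up to Week 12. It needs an AE that began in a screening period of at most 28 days, was still ongoing at first dose, and then changed.
- **That placebo events become GLPG0634 events in the main safety comparison.** The seven-arm tables stop at Week 12, so the switch cannot touch them. The switch columns are labelled as treatment sequences (SAP 2.1.2) and are descriptive only (SAP 4.5.3). The total shown for data after Week 12 is across all groups, not across GLPG0634 groups (SAP 2.4.2). An AE of unchanged intensity stays in its first period.
- **That the protocol's AE definition rules out an easing record.** The definition says "This includes any occurrence that is new in onset or aggravated in intensity or frequency from the baseline condition". That is an inclusion under a broad definition, not a requirement, and the comparison is with the condition at consent, not with the last recorded intensity.
- **That a percentage inflation can be estimated.** It would need the share of subjects with AEs ongoing at each boundary and the share that later ease. Neither is in the documents. Using all later intensity changes instead would count true worsenings as spurious.

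Two further points are fair. The eCRF completion instructions and the mock tables are not available, so a linking rule there cannot be excluded. The SAP also leans deliberately towards over-attribution, for example when an AE start date is incomplete or relatedness is missing, and the listings allow continuations to be traced by hand.

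The limits on reach stand in full. The worst-case argument does not: those rules resolve missing information, whereas here dates and intensities are known and an improvement is still scored as an emergence.

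**Conclusion.** The gap is real but narrow. As written, the plan miscounts at subject level in two places: a screening-onset AE that eases after first dose is counted as a TEAE in whichever arm the subject is in, and a first-period AE that eases after the Week 12 visit is counted again in the second-12-weeks tables. The second applies to non-switching columns too, but it matters most for placebo and low-dose switchers, where treatment has changed.

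Other within-period counts, full-24-weeks counts for events starting after first dose, AEs of unchanged intensity, and all efficacy analyses are unaffected.

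The size cannot be put higher than scale: about 3 to 4 percentage points on a second-period rate per affected subject in a placebo-switch column, given the planning ACR20 rates and an assumed 1:1 split. The conclusion rests on the new record carrying the date of the intensity change as its start date. It should be corrected, but it does not threaten the trial's main conclusions.

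**What to change.** In SAP 12.1.1, add a linking rule. Within a subject, chain records of the same preferred term whose stop and start dates are contiguous. Count a later record as emergent in a period only if its intensity exceeds the worst intensity of that event before the period. Otherwise it keeps the onset date and period of the first record in the chain. Confirm against the eCRF instructions how the start date of an intensity-change record is entered.

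The cost is a few lines of SAP text and some AE programming. Term, dates and intensity are already collected, so no new data are needed. The drawback is a small risk of merging two distinct back-to-back episodes of the same term; these would remain visible in Listings 16.2.10.1 and 16.2.10.2.

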### 12.1.2. Treatment Relatedness

Following (ICH-E3), the investigator's assessment of drug relatedness will be dichotomized as follows:

Drug related: at least possibly drug related, OR with missing drug relatedness (= worst-case)

Not drug related: less than possibly drug related.

In tabulations this dichotomized parameter will be used, but in the listings the original parameter will be presented. Note that there is only the drug-relatedness assessment by the investigator.

### 12.1.3. Worst-Case Principle

When cross-tabulating AE preferred terms versus an AE attribute (e.g., intensity), the worst-case is always applied within each analysis period. I.e., when a subject has two times the same AE preferred term in the same analysis period, then the subject is reported only once: only with the worst intensity. If this happens in two different analysis periods, the AE is reported twice: once in each analysis period.

### 12.1.4. Adverse Event Onset Day and Duration

#### AE onset day in the study

= (AE start date) – (date of first study drug administration) + 1, when the AE start date is completely known;

= missing when the AE start date is incomplete or unknown.

#### AE onset day in the period

= (AE start date) – (start date of the period into which the AE was allocated) + 1, when the AE start date is completely known;

= missing when the AE start date is incomplete or unknown.

#### AE duration

= (AE stop date) – (AE start date) + 1, when both dates are completely known;

= (trial termination date) – (AE start date) + 1, when the AE start date is fully known but the AE is not resolved at the end of the study; in this case the duration will be presented as ">x days" in the listing to identify it as a censored result;

= missing when the AE start date is incomplete or unknown, or when the AE has resolved but with an incomplete or unknown end date.

### 12.1.5. Calculation of Percentages

All percentages will be calculated against the total number of subjects that are still in the study in that particular analysis period.

### 12.1.6. Tables up to Week 12

No formal inferential statistics (p-values) will be derived.

An as-treated analysis will be performed. All tabulations and listings will present treatments rather than analysis periods.

#### **Table 14.3.1.1: Treatment-emergent adverse events up to Week 12: Summary table**

Tabulation per treatment of the number and percentage of subjects with the following:

- Subjects with at least one treatment-emergent adverse event (TEAE)
- Subjects with at least one serious TEAE
- Subjects who died (treatment-emergent)
- Subjects with at least one mild TEAE as worst intensity
- Subjects with at least one moderate TEAE as worst intensity
- Subjects with at least one severe TEAE
- Subjects with at least one TEAE that was considered treatment-related
- Subjects with at least one treatment-emergent SAE that was considered treatment-related
- Subjects with at least one TEAE for which the study treatment was temporarily stopped
- Subjects with at least one TEAE for which the study treatment was permanently stopped
- Subjects with at least one TEAE flagged as an individual stopping criterion by the investigator.

Population: safety.

Table to be created for the Week 12 interim analysis as well.

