#### **8.3.4 Removal of Subjects from Therapy or Assessments**

Subjects may stop study medication for any of the following reasons:

- Subject request.
- Use of non-permitted concurrent therapy.
- Noncompliance with the study medication (see Section 8.5.9).
- Noncompliance with the study procedures (see Section 8.5.9 and Section 8.6).
- Lost to follow-up.
- Occurrence of AEs not compatible with the continuation of subject participation in the study, in the investigator's opinion. This also includes any clinically significant laboratory results, ECGs and vital signs.
- Investigator request.
- Sponsor request.
- Treatment failure deemed by the investigator as lack of improvement or worsening of the disease symptoms or occurrence of intolerable AEs.

Treatment with GLPG0634 will be discontinued and the subject withdrawn from this study for:

- Serious infections (those requiring parenteral antimicrobial therapy or hospitalization).
- Any opportunistic infections.
- Complicated herpes zoster infection (multi-dermatomal, disseminated, ophthalmic or CNS involvement).
- Two sequential total white cell counts  $<2000$  cells/mm^3 (SI:  $<2.0 \times 10^9$  cells/L).
- Two sequential neutrophil counts  $<1000$  neutrophils/mm^3 (SI:  $<1.0 \times 10^9$  cells/L).
- Two sequential lymphocyte counts  $<750$  lymphocytes/mm^3 (SI:  $<0.75 \times 10^9$  cells/L).
- Two sequential hemoglobin  $<8.0$  g/dL (SI:  $<80$  g/L).
- Two sequential platelet counts  $<75,000$  platelets/mm^3 (SI:  $<75.0 \times 10^9$  cells/L).
- Two sequential AST or ALT elevations  $>3$  times the upper limit of normal with at least one total Bilirubin value  $>2$  times the upper limit of normal.
- Two sequential AST or ALT elevations  $>3$  times the upper limit of normal accompanied by symptoms consistent with hepatic injury.

- 
- Two sequential AST or ALT elevations >3 times the upper limit of normal accompanied by elevated INR.
  - Two sequential AST or ALT elevations >5 times the upper limit of normal, regardless of total Bilirubin or accompanying symptoms.
  - Two sequential increases in serum creatinine >50% over the average of screening and baseline values.
  - Two sequential decreases from the baseline of inhibin B by 50% or testosterone by 50% with concurrent increases in FSH or LH respectively.

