**Table 14.3.1.12: Treatment-emergent adverse events up to Week 12: Tabulation of the drug-relatedness of serious events**

Cross-tabulation of TEAE preferred terms versus their drug-relatedness; per body class and per treatment group. Selecting only the treatment-emergent serious adverse events.

Population: safety.

Table to be created for the Week 12 interim analysis as well.

**Table 14.3.1.13: Treatment-emergent adverse events up to Week 12: Tabulation of the drug-relatedness of events leading to discontinuation**

Cross-tabulation of TEAE preferred terms versus their drug-relatedness; per body class and per treatment group. Selecting only the TEAEs for which the study treatment was permanently discontinued (AE page), or for which the study was discontinued (trial termination page).

Population: safety.

Table to be created for the Week 12 interim analysis as well.

**Table 14.3.1.14: Treatment-emergent adverse events up to Week 12: Tabulation of the drug-relatedness of events leading to a temporary stop**

Cross-tabulation of TEAE preferred terms versus their drug-relatedness; per body class and per treatment group. Selecting only the TEAEs for which the study treatment was temporarily stopped (AE page).

Population: safety.

**Table 14.3.1.15: Treatment-emergent adverse events up to Week 12: Tabulation of the drug-relatedness of individual stopping rules**

Cross-tabulation of TEAE preferred terms versus their drug-relatedness; per body class and per treatment group. Selecting only the TEAEs that were flagged as “stopping criterion” in the eCRF by the investigator.

Population: safety.

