### 12.2.4. Baseline and Change from Baseline

The baseline is defined as the last sample prior to first dosing, so should normally be from the Day -1 visit. Baseline will be determined per lab test individually. It is recognized that baseline tests may thus come from more than one lab sample and not just from the “baseline visit” sample.

The change from baseline will be calculated for all post-baseline time points as:

Change from baseline at time point t = value at time point t – baseline value.

The percentage change from baseline will be calculated for all post-baseline time points as:

Percent change from baseline at time point t = 100 x (change from baseline at time point t / baseline value).

Note that the percent change from baseline will be left missing in case the baseline value is zero.

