**Table 14.3.2.11: Laboratory data up to Week 12: Treatment-emergent ATP III classes per time point**

Frequency table of the treatment-emergent lab ATP III classes per lab test category (hematology, biochemistry), lab test, treatment group and time point (including worst-case). A post-baseline class is considered treatment-emergent if it differs from the baseline result and is of higher category.

Table for selected tests only.

Population: safety.

Table to be created for the Week 12 interim analysis as well.

**Table 14.3.2.12: Laboratory data up to Week 12: Frequency table of percent changes from baseline per time point in inhibin B and testosterone**

Frequency table of the percent changes from baseline per lab test category (endocrine), lab test, treatment group and time point. The percent changes from baseline will be categorized

as: <-50%, [-50%,+50%], >+50%. A worst-case will also be shown selected as the lowest post-baseline value.

Table only for inhibin B, free testosterone, total testosterone.

Population: safety – males.

Population: safety, selecting male subjects with a baseline value within normal range.

Table to be created for the Week 12 interim analysis as well.

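### The SAP never derives the protocol's laboratory stopping criteria from the lab data: it counts investigator flags only, and the planned lab tables do not fill the gap

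*SAP*

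**What the plan says.** Protocol Section 8.3.4 requires discontinuation and withdrawal when any of a list of limits is met. Eleven are laboratory limits: white cells, neutrophils, lymphocytes, hemoglobin, platelets, four ALT/AST conditions, creatinine, and the male hormones. Each rests on two sequential results, for example "Two sequential increases in serum creatinine >50% over the average of screening and baseline values". A first abnormal result triggers an unscheduled retest within 3 to 5 days. Hematology and chemistry go to a central laboratory (Section 8.7.1.4.2).

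In the SAP, the stopping-criterion row of the adverse event summary (Table 14.3.1.1) is "Subjects with at least one TEAE flagged as an individual stopping criterion by the investigator". Table 14.3.1.15, titled as a "Tabulation of the drug-relatedness of individual stopping rules", is built by "Selecting only the TEAEs that were flagged as “stopping criterion” in the eCRF by the investigator". Tables 14.3.1.16 and 14.3.1.30 repeat this for 24 weeks, and the narrative listing (16.2.10.7) takes its stopping-criterion entry from the same flag.

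Laboratory values are reported separately: by normal range, by CTCAE v3.0 grade (SAP 12.2.5.2 and 12.2.5.3), and as change from a baseline for which "The baseline is defined as the last sample prior to first dosing, so should normally be from the Day -1 visit". Inhibin B and testosterone have their own percent-change table (14.3.2.12), where "A worst-case will also be shown selected as the lowest post-baseline value".

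**The concern.** The laboratory limits are objective and the data are collected centrally, yet the count of subjects who met them depends on an investigator recognising the event, recording it as an adverse event and ticking a box. Protocol Section 8.7.1.4.1.1 allows a laboratory abnormality to be an adverse event, but nothing obliges each limit to become a flagged one. A subject who met a limit but was neither flagged nor taken off drug, and had no serious event, would enter no stopping-criterion count and no narrative listing.

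In a dose-finding trial that affects two things: how often each regimen reaches the protocol's own limits, and whether the drug was stopped when it should have been. A difference between arms in flag counts would mix drug effect with reporting practice.

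**Working it through.** No stated figure in the plan needs reproducing here. The check sets each protocol limit against the SAP's categories.

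**1. Limits against grade boundaries** (protocol 8.3.4; SAP 12.2.5.2, 12.2.5.3 and Table 14.3.2.12)

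| Protocol limit | SAP cut points | Result |
|---|---|---|
| White cells <2.0 | 3.0, 2.0, 1.0 | coincides |
| Neutrophils <1.0 | 1.5, 1.0, 0.5 | coincides |
| Hemoglobin <80 g/L | 100, 80, 65 | coincides |
| Platelets <75 | 75, 50, 25 | coincides |
| ALT/AST >5 x ULN | 1, 2.5, 5, 20 | coincides |
| Lymphocytes <0.75 | 0.8, 0.5, 0.2 | inside grade 2 |
| ALT/AST >3 x ULN (three criteria: with bilirubin >2 x ULN, symptoms, or INR) | ALT/AST 1, 2.5, 5, 20; bilirubin 1, 1.5, 3, 10 | both inside grade 2; not combined |
| Creatinine >50% over average | multiples of ULN | no relative category |
| Inhibin B or testosterone down 50% with FSH or LH rise | <-50%, [-50%,+50%], >+50% | fall tabulated; exactly -50% sits in the middle class; no pairing |

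Five of the 11 coincide, on single values. The worst-case rule (SAP 12.2.8) does include unscheduled retests, but takes the worst single value. No SAP table asks whether two consecutive results met a limit.

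**2. What merging means.** ALT 4 x ULN with bilirubin 2.5 x ULN prints as two separate grade 2 entries. So does ALT 2.6 x ULN with bilirubin 1.6 x ULN, which meets neither limit.

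**3. Creatinine grade.** Let m be the screening/baseline average as a multiple of ULN. A rise just over 50% gives 1.5m, and grade 0 needs a value no higher than 1.0, so m must be below 1/1.5 = 0.667. At +51%:
- m = 0.60: 1.51 x 0.60 = 0.906, grade 0
- m = 0.66: 0.997, grade 0
- m = 0.67: 1.012, grade 1
- m = 0.90: 1.359, grade 1

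With an assumed ULN of 90 µmol/L (the documents give none), 55 rising to 85 is (85 - 55)/55 = 54.5%. The average is 55/90 = 0.611 x ULN, and the result prints as grade 0 and normal. It would also be absent from the abnormalities listing, which takes only out-of-range results.

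**4. Creatinine baseline.** Illustrative values:
- Screening 60, baseline 80: average 70, limit 1.5 x 70 = 105. On the SAP baseline this is (105 - 80)/80 = 31.3%.
- Screening 80, baseline 60: same limit of 105. On the SAP baseline this is (105 - 60)/60 = 75.0%.

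The SAP's percent change therefore cannot be read against the protocol limit, and that table has no creatinine categories.

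**The case against.** The strongest reply is that a recognised hit has several routes into the output. Withdrawal is mandatory, so it should appear among events leading to discontinuation (Table 14.3.1.13) and termination reasons (Table 14.1.1.7), and in the discontinuation listing, which expressly includes the stopping rules. The full laboratory listing holds every value. Protocol Section 6.5 describes the criteria as guidance to investigators, and DSMB outputs, the Protocol Deviation Plan and the table shells are separate documents not seen here. All of this stands. It limits the gap to hits that were not recognised or not flagged, but none of the outputs seen here would count them.

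Four stronger readings are tempting, and the documents do not support them:

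- **That subjects over a limit generally look normal.** This is shown only for creatinine. ALT/AST above 3 x ULN and bilirubin above 2 x ULN print as grade 2 or worse, as do lymphocytes below 0.75 if the lower limit of normal is at least 0.8. Those hits are blurred, not hidden.
- **That the hormone criterion is unreported.** Falls beyond 50% are tabulated by group in Table 14.3.2.12; the sequential rule and the FSH/LH pairing are what is missing.
- **That this count is the main tolerability read-out.** Protocol 8.8.1.4 and SAP 6.1.3 describe safety through adverse events, laboratory data, ECG, vital signs and physical examination, and give this count no such rank.
- **That the Week 12 interim should carry the new table.** SAP version 5.0 records changes made after the interim lock (6.3.2), so that is past.

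It is also fair that not every criterion can be programmed from its wording alone. Hepatic symptoms are not laboratory data, and elevated INR and concurrent FSH/LH increases have no stated magnitude.

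**Conclusion.** The point holds as a gap in the safety analysis. Every stopping-criterion count in the SAP depends on the investigator's flag, no table applies the two-sequential rule, and six of the 11 laboratory criteria have no matching category or combination. One of those six needs symptoms and cannot come from laboratory data alone. Creatinine is the sharpest case: a subject whose screening/baseline average is below 0.667 x ULN can meet the limit and print as grade 0 and normal.

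How many subjects this affects cannot be judged from the documents. It depends on how completely investigators reported, and on the laboratory's normal limits, which are not given. The lymphocyte statement assumes a lower limit of normal of at least 0.8. The improvement is worth making because it is cheap and uses data already collected; it does not bear on the primary efficacy analysis.

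**What to change.** For the final analysis, derive each laboratory criterion of protocol Section 8.3.4 from the central-laboratory data as the protocol words it, including unscheduled retests, with the screening/baseline average for creatinine and the joint conditions for ALT/AST with bilirubin or INR and for the hormones with FSH or LH. Tabulate by treatment group the number of subjects who:

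- met the limit once
- met it on two sequential results
- were flagged by the investigator
- had study drug stopped

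Present this beside Tables 14.3.1.15 and 14.3.1.30, not in place of them. Keep the investigator flag for symptoms, infections and the other non-laboratory criteria.

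Reconcile the two creatinine reference values (protocol 8.3.4 and SAP 12.2.4) by stating which applies to which output. Write down the programming conventions for an elevated INR, a concurrent FSH/LH increase, a hormone fall of exactly 50%, and a missing retest.

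The cost is modest extra programming plus agreement on those conventions. No new assessments are needed, and no threshold or clinical rule changes.
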